With the current standard-of-care (*i.e.*, control arm), patients make up to 4 health center visits to complete TB diagnostic evaluation (**Figure 2**). At the first visit, sputum is collected for smear microscopy. All patients are required to return for a second visit; patients are initiated on TB treatment if the first sputum is smear-positive or are asked to provide a second sputum specimen and return for a third visit to collect results if the first sputum is smear-negative. Patients who return for a third visit are initiated on TB treatment if the second sputum is smear-positive or are asked to provide a third sputum specimen that is sent out for Xpert testing. Patients are asked to return for a fourth visit to collect Xpert results. Patients who return for a fourth visit are initiated on TB treatment if Xpert results are positive (or referred to an MDR TB treatment center if Xpert testing indicates rifampin resistance). Of note, HIV-infected patients have sputum collected for Xpert testing at their first visit and all patients could be started on TB treatment empirically at any visit.

The intervention strategy seeks to facilitate diagnosis and treatment of TB at the initial health center visit (or referral of patients to MDR TB treatment center if rifampin resistance is detected by Xpert). As further described below, it includes the following components: 1) onsite molecular

testing as a replacement for microscopy; 2) process re-design; and 3) feedback of TB diagnostic evaluation quality indicators to health center staff.

Figure 2. Comparison of TB diagnostic evaluation in the intervention and control arms

*Consider empiric treatment or additional testing if test results are negative or invalid

On-Site Molecular Testing

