- **Number enrolled:** Number of eligible patients identified over a defined enrolment period through review of the NTLP Presumptive TB register, NTLP Laboratory register, GeneXpert laboratory requisition forms, GxAlert database and NTLP Treatment register at each study site (includes patients treated for TB without undergoing any sputum testing).
- **Date enrolled:** Earliest date recorded in the NTLP Presumptive TB register, NTLP Laboratory register, GeneXpert laboratory requisition form, GxAlert database, or NTLP Treatment register. Records will be prospectively reviewed using name, sex, and age to identify patients presenting multiple times over the study period. Visits occurring within six months of the initial presentation will be considered as part of the same episode.
- **Number referred for testing:** Number of eligible patients identified through review of the NTLP Presumptive TB register, NTLP Laboratory register, GeneXpert laboratory requisition forms, and GxAlert database at each study site.
- **Number tested:** Number of eligible patients with any smear or Xpert result entered into the NTLP Presumptive TB register, NTLP Laboratory register, GeneXpert laboratory requisition forms, NTLP treatment register, or GxAlert database at each study site.
- **Number completing testing:** Number of eligible patients with one valid Xpert result plus number of eligible patients with a valid smear result entered into the NTLP Presumptive TB register, NTLP Laboratory register, GeneXpert laboratory requisition forms, GxAlert database, or NTLP treatment register. Definitions of valid results are as follows:
 - A positive Xpert result with a semi-quantitative result of high, medium, low, or very low for all patients; a positive Xpert Ultra result with a semi-quantitative result of trace for HIV-positive patients; or second positive Xpert Ultra result if the initial result is trace-positive for HIV-negative patients;
 - A negative Xpert or Xpert Ultra result for all patients;³¹
 - One positive or two negative smear results for HIV-negative/HIV status unknown patients.
- **Number diagnosed:** Number of eligible patients with microbiologically-confirmed TB via a positive smear and/or Xpert test result entered into the NTLP Presumptive TB register, NTLP Laboratory register, GeneXpert laboratory requisition forms, NTLP treatment register, and/or GxAlert database within 6 months of *date enrolled*.

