3.3 Interventions

Intervention arm: Health centers randomized to the intervention arm will receive the following intervention components: 1) onsite molecular testing for TB with GeneXpert as a replacement for sputum smear microscopy; 2) process redesign to facilitate same-day TB diagnosis and treatment; and 3) performance feedback of TB diagnostic evaluation quality indicators to health center staff.

Control arm: Health centers randomized to the control arm will follow the standard-of-care TB evaluation strategies, which are onsite ZN or LED fluorescence microscopy and hub-based GeneXpert testing for selected patients in accordance with Uganda NTLP guidelines.

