- **Number completing testing:** Number of eligible patients with a valid Xpert result plus number of eligible patients with a valid smear result entered into the NTLP Presumptive TB register, NTLP Laboratory register, GeneXpert laboratory requisition forms or NTLP treatment register, or with a test result recorded in the GeneXpert machine data. Testing must be completed within six months of enrolment. If the test result is missing and cannot be found in the GeneXpert machine data, it will be assumed that the patient was tested within six months of enrolment. Definitions of valid results are as follows:
 - A positive Xpert (Ultra) result with a semi-quantitative result of high, medium, low, or very low for all eligible patients; a positive Xpert Ultra result with a semi-quantitative result of trace for eligible HIV-positive patients; or a second positive Xpert Ultra result (including trace) if the initial result is trace-positive for eligible HIV-negative patients;⁶

- A negative Xpert result for all eligible patients;
- One positive OR two negative smear results for eligible HIV-negative/HIV status unknown patients.

- **Microbiologically-confirmed TB:** A positive smear and/or positive Xpert test result (as defined above) entered into the NTLP Presumptive TB register, NTLP Laboratory register, GeneXpert laboratory requisition forms, NTLP treatment register, and/or GeneXpert machine data (intervention sites only) within six months of enrolment. **Number diagnosed:** Number of eligible patients with microbiologically-confirmed TB via a positive smear and/or valid Xpert test result entered into the NTLP Presumptive TB register, NTLP Laboratory register, GeneXpert laboratory requisition form, NTLP treatment register, and/or GeneXpert machine data within six months of enrolment.
- **Number with RIF resistance detected by Xpert:** Number of eligible patients with RIF resistance identified by Xpert testing entered into the GeneXpert laboratory requisition forms and/or NTLP Laboratory registers within six months of enrolment .
- **Number with RIF resistance confirmed by culture:** Number of eligible patients with: (1) RIF resistance detected by Xpert testing entered into the GeneXpert laboratory requisition forms and/or NTLP Laboratory registers, and (2) RIF resistance confirmed by culture-based DST or a second molecular assay as determined by review of Lab Register at MDR treatment center within six months of enrolment .

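### As worded, the number completing testing adds Xpert and smear patients, so HIV-negative or HIV-unknown patients with both valid could be counted twice, mainly in the control arm

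*Combined protocol and SAP*

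**What the plan says.** The amended SAP, section 3.4, defines *Number completing testing* as "Number of eligible patients with a valid Xpert result plus number of eligible patients with a valid smear result". SAP version 1.0 (section 3.4) and both protocol versions (Outcomes, Definitions) have the same sum: "Number of eligible patients with one valid Xpert result plus number of eligible patients with a valid smear result". Neighbouring definitions in the amended SAP join the tests differently: *Number tested* uses 'or', and *Microbiologically-confirmed TB* uses 'and/or'. Section 2.3 says that the SAP takes precedence over the protocol.

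Two further rules in the amended SAP belong to the same definition:

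- A valid smear is "One positive OR two negative smear results for eligible HIV-negative/HIV status unknown patients". No smear result is valid for an HIV-positive patient.
- On missing data: "If the test result is missing and cannot be found in the GeneXpert machine data, it will be assumed that the patient was tested"; the time limit is six months. The parallel sentence under *Number tested* is triggered by a missing result date, not a missing result.

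On the pathways, the protocol (Intervention and Control (Wait-list) Arms) says that control patients whose second smear is also negative "are asked to provide a third sputum specimen that is sent out for Xpert testing". SAP section 3.3 describes control testing as "onsite ZN or LED fluorescence microscopy and hub-based GeneXpert testing for selected patients in accordance with Uganda NTLP guidelines" and the intervention as "onsite molecular testing for TB with GeneXpert as a replacement for sputum smear microscopy".

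The count is the numerator of the secondary outcome *Proportion completing testing*. That outcome is also analysed by HIV status and sex with interaction P-values (section 4.4.5, Annex Table 5c). The count itself is listed among the post-hoc analyses.

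**The concern.** A proportion needs each patient to count at most once. A sum of two overlapping groups does not ensure this, and here the overlap depends on the arm. The control pathway produces patients with two negative smears and an Xpert result. The intervention pathway replaces smear, so overlap there should be rare. Applied literally, the rule would raise the control proportion and pull the risk ratio down, against the intervention. Because overlap cannot occur in HIV-positive patients, it could also create or mask an interaction by HIV status.

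The other two rules create inconsistencies of their own. The missing-data sentence assumes testing for a patient with no result, although the definition requires a valid one. The smear rule leaves out an HIV-positive, smear-positive patient without a valid Xpert, although *Number diagnosed* accepts a positive smear with no HIV restriction of its own. Such a patient could count in the primary outcome without having completed testing, so the cascade would not be nested.

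**Working it through.** **Figure to reproduce.** The plan gives no expected value, event count or power for this outcome. The only scale used below is its harmonic mean of 268 patients per cluster (section 3.5); 20 × 268 = 5360, which matches its planned enrolment.

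**Step 1: who can be in both groups.** Take a control patient of negative or unknown HIV status. Two negative smears are a valid smear result. The patient is then asked for a third specimen for Xpert, and a valid result there places the patient in both terms. One positive smear plus a valid Xpert would do the same. HIV-positive patients cannot be in both, because none of their smears is valid under this rule.

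**Step 2: size of the excess.** By inclusion-exclusion,

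N(Xpert valid) + N(smear valid) = N(either valid) + N(both valid).

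The over-count is exactly the number with both. Let u be the share of enrolled controls with either result valid and f the share with both. The literal control proportion is u + f instead of u. If overlap occurs only in the control arm and u and f are the same in every cluster, the risk ratio (intervention over control) is multiplied by u/(u + f).

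**Step 3: range.** The documents give neither u nor f. Assume u = 0.70, so the once-only count is 268 × 0.70 = 188 per cluster. The last column further assumes an intervention proportion of 0.90, for which the once-only risk ratio is 0.90/0.70 = 1.29.

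| f (assumed) | Counted per 268 | Control proportion | Multiplier u/(u + f) | Risk ratio as counted |
|---|---|---|---|---|
| 0.05 | 201 | 75% | 0.70/0.75 = 0.93 | 1.20 |
| 0.10 | 214 | 80% | 0.70/0.80 = 0.88 | 1.13 |
| 0.20 | 241 | 90% | 0.70/0.90 = 0.78 | 1.00 |
| 0.30 | 268 | 100% | 0.70/1.00 = 0.70 | 0.90 |

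When u + f exceeds 1 the result is not a proportion: u = 0.80 with f = 0.30 gives 110%.

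**Step 4: HIV sub-groups.** In HIV-positive patients the multiplier is 1. In HIV-negative patients it is u/(u + f) for that group. With no true interaction, the ratio of the two risk ratios (HIV-negative over HIV-positive) would therefore equal that multiplier: 0.93 to 0.70 if the values in Step 3 held among HIV-negative controls.

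**Step 5: unadjusted against adjusted.** The unadjusted analysis of proportions (section 4.4.4.2) starts from a cluster risk, which could be computed from the literal sum. The individual-level adjustment, if its completeness and imbalance conditions are met, fits a logistic model and so needs a 0/1 outcome for each patient. The two risk-ratio columns of Annex Table 5b could then estimate different quantities.

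**Step 6: missing results.** If the sentence were applied as completion, a share m of enrolled patients with no result would be added. From an assumed 60%, m = 0.05 to 0.20 (assumed) gives 65% to 80%. The documents do not say how m differs by arm.

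**Step 7: HIV-positive, smear-positive, no valid Xpert.** If these are 0.5% to 2% of those enrolled (assumed), 268 × 0.005 = 1.3 to 268 × 0.02 = 5.4 patients per cluster would be left out. This would fall mainly on the control arm, where smear is routine, and would lower its proportion.

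**The case against.** The best defence is that the sum describes two routes to completion, with each patient counted once. The definition counts eligible patients. Data Management creates one REDCap record per patient. Section 4.4.4.2 analyses a risk and adjusts it with a patient-level logistic model, and Table 5b reports n/N. None of this fits a count that can exceed 100%. This stands as evidence of intent. A reader might infer that control patients are in fact counted twice; the documents do not show that. But the governing text still states the sum, all four definitions have it, and the adjacent definitions show that the authors had other connectors to hand.

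The overlap may also be small. Hub Xpert is for selected patients. On the smear-first route, overlap through two negative smears requires two return visits and a third specimen. The protocol's Background says that many patients do not return, and its formative interviews report that second samples are often not brought. That argues for the lower end of the range and against treating 110% as an expected result.

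The missing-data sentence looks like a slip: it follows a six-month limit and concludes only that the patient was tested in that time. The HIV restriction on smear may be partly deliberate, since HIV-infected control patients have sputum collected for Xpert at the first visit, and not accepting their negative smears as complete is coherent. The clear inconsistency is confined to their positive smears. Even there, the words 'as defined above' under *Microbiologically-confirmed TB* leave room for another reading.

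**Conclusion.** The concern holds as a defect of wording that could bias one secondary outcome. Under the stated assumptions (70% of controls with either result valid, 5% to 30% with both, overlap in the control arm only) the control proportion would read 75% to 100% and the risk ratio would be multiplied by 0.93 to 0.70. Taken alone, the double count works against the intervention, so it would not manufacture a benefit. The smear restriction acts in the opposite direction, and the effect of the missing-result rule by arm is unknown, so the net bias of the three rules cannot be signed.

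The reach is narrow: *Proportion completing testing*, its sub-groups, and the post-hoc *Number completing testing*. A reader might infer that the main result is in doubt because testing comes early in the cascade. The documents do not support that. The primary outcome and the sample size do not use this definition, and the SAP's account of the cascade puts screening before testing.

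**What to change.** Make three changes in section 3.4 of the SAP, with matching text in the protocol:

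1. Define a patient-level yes/no flag: at least one valid Xpert result OR a valid smear result, each patient counted once. Use this flag for the cluster risks, the observed-to-expected ratios, the sub-groups and the post-hoc count.
2. In the missing-data sentence, replace the missing test result with a missing test result date, as under *Number tested*.
3. Reconcile the HIV restriction on valid smears with *Number diagnosed*. One option is to count a positive smear as completed testing for this outcome whatever the HIV status, so that diagnosed patients are a subset of those completing testing. This concerns only how the outcome is counted, not which test a patient should have.

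The cost is a few lines of text and no new data. If the analysis has already been run, state which rule was coded, and give the number of patients per arm with both results valid. The protocol promises public participant-level data and code, so re-analysts will rely on the written definition.

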3.4 Outcomes

Definitions used to assess study outcomes

- **Eligible patient:** clinic attendees satisfying our inclusion and exclusion criteria (as listed above) AND excluding patients aged <18 years or those with a documented prior history of TB treatment (e.g., reason for Xpert testing or TB treatment marked as treatment failure, relapse, treatment after loss to follow-up, etc.). In addition, patients identified as RIF resistant by Xpert testing will not contribute to the primary and secondary analysis except for the number and proportion with RIF resistance detected by Xpert or RIF resistance confirmed by culture.
- **Number enrolled (i.e., number evaluated for TB):** Number of eligible patients identified over a defined enrolment period through review of the NTLP Presumptive TB register, NTLP Laboratory register, GeneXpert laboratory requisition forms and NTLP Treatment register at each study site (includes patients treated for TB without undergoing any sputum testing).
- **Date enrolled:** Earliest date recorded in the NTLP Presumptive TB register, NTLP Laboratory register, GeneXpert laboratory requisition form, NTLP Treatment register or machine data. Records will be prospectively reviewed using name, sex, and age to identify patients presenting multiple times over the study period. Visits occurring within six months of enrollment will be considered as part of the same episode.
- **Number referred for testing:** Number of eligible patients identified through review of the NTLP Presumptive TB register, NTLP Laboratory register and GeneXpert laboratory requisition forms at each study site. Patients indicated as new in the NTLP Treatment Register will also be considered testing referrals.
- **Number tested:** Number of eligible patients with any smear or Xpert result entered into the NTLP Presumptive TB register, NTLP Laboratory register, GeneXpert laboratory requisition forms, or NTLP treatment register at each study site, or with a test result recorded in the onsite GeneXpert machine. Results must be dated within six months of enrolment. If result date is missing and cannot be found in the GeneXpert machine data, it will be assumed that the patient was tested within six months of enrolment.

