- **Number treated:** Number of eligible patients entered into the NTLP Treatment register as having started Category I or II regimen.
- **Number completing treatment:** Number treated and with a treatment outcome of cured or completed entered into the NTLP Treatment register.
- **Number died, among those initiated on TB treatment:** Number treated and with a treatment outcome of died entered into the NTLP Treatment register within six months of enrolment , or number treated and confirmed dead by next of kin with a date of death within six months of enrolment.
- **Number died, among those with confirmed TB:** Number diagnosed and with a treatment outcome of died entered into the NTLP Treatment Register within six months of enrolment, or number diagnosed and confirmed dead by next of kin with a date of death within six months of enrolment.
- **Number died, among all those eligible:** Number treated and with a treatment outcome of died entered into the NTLP Treatment register within six months of enrolment, or number traced with a death recorded
- **Time-to-diagnosis:** Number of days from *date enrolled* to earliest date of positive smear or valid Xpert result recorded in NTLP Presumptive TB register, NTLP Laboratory register, GeneXpert laboratory requisition form, or NTLP treatment register within six months of enrolment . For the control arm, attempts will be made to abstract the missing Xpert result dates from machine data from GeneXpert machines at testing hubs. For patients with microbiologically confirmed TB who are missing the smear or Xpert result date, the date of treatment initiation will be used as the date of diagnosis.
- **Time-to-treatment:** Number of days from *date enrolled* to treatment start date entered into NTLP Treatment register if treatment start date is within six months of enrolment.

Primary Outcome

Outcome	Numerator	Denominator
Number treated for microbiologically-confirmed TB within 14 days of date enrolled.	Number diagnosed and time-to-treatment within 14 days	None

Secondary Outcomes

A. Testing		
Outcome	Numerator	Denominator
Number referred for TB testing	Number referred for testing	None
Proportion completing testing	Number completing testing	Number enrolled
B. Diagnosis		
Outcome	Numerator	Denominator
Number diagnosed with microbiologically-confirmed TB*	Number diagnosed	None
Proportion diagnosed with microbiologically-confirmed TB*	Number diagnosed	Number enrolled

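### SAP 3.4 gives two rules on whether GeneXpert machine data can confirm TB in control clinics, so the primary event could be ascertained from different sources in the two arms

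*Combined protocol and SAP*

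**What the plan says.** All of this is in section 3.4 of the amended SAP (the version that closes with a Table of Amendments).

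- **Microbiologically-confirmed TB** is a positive smear or Xpert result in the registers, the requisition forms, "NTLP treatment register, and/or GeneXpert machine data (intervention sites only) within six months of enrolment".
- **Number diagnosed** follows directly. It counts eligible patients with microbiologically-confirmed TB, but its own source list ends "NTLP treatment register, and/or GeneXpert machine data within six months of enrolment", with no arm limit.
- **Number completing testing** also has no arm limit: "or with a test result recorded in the GeneXpert machine data".
- **Primary outcome.** The name is "Number treated for microbiologically-confirmed TB within 14 days of date enrolled" and the numerator is "Number diagnosed and time-to-treatment within 14 days". The name uses the restricted term and the numerator uses the unrestricted one.
- **Trace results.** For HIV-negative patients a trace result is valid only with "a second positive Xpert Ultra result (including trace) if the initial result is trace-positive for eligible HIV-negative patients".

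The time-to-diagnosis definition says that the trial will try to obtain hub machine data for control patients, but only to fill in missing result dates. Section 4.4.3 plans two sensitivity analyses of the primary outcome. Both reclassify trace results, and both are run only if the trace share is similar in the two arms.

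**The concern.** Two consecutive definitions disagree on what can confirm a primary event in a control clinic. An analyst who codes the confirmed-TB definition literally gives intervention clinics five sources for a positive result (three registers, the requisition form and the machine) and control clinics four. The primary outcome is a count with no denominator, so an event missed in one arm passes straight into the ratio. The trial is open-label and rests on routine records, so it depends on finding events in the same way in both arms. The baseline-count covariate would not correct a difference, because it covers the 12 months before 22 October 2018, before onsite devices were in use.

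**Working it through.** **1. Which rule governs.** The numerator is number diagnosed, whose own list has no arm limit. That favours machine data in both arms. The log entry dated 4 March 2020, used here only as a pointer to intent, says the same. But number diagnosed is defined through microbiologically-confirmed TB, which carries the limit. The text therefore permits either coding, and the conflict stands without the log.

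**2. The plan's own figure.** SAP Table 3 gives detectable geometric mean ratios of 1.30 and 1.36 (SD 0.2; 80% and 90% power) and 1.49 and 1.58 (SD 0.3). With 10 clinics per arm less the one added for stratification, n = 9, and two-sided 5% assumed:

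exp{SD × √(2/9) × (z₀.₉₇₅ + z_power)} = 1.302, 1.357, 1.486, 1.582.

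The table reproduces, and this point does not affect it.

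**3. Effect of the bracket on the ratio.** Let g be the share of control primary events whose only positive result is in hub machine data. If these are lost in control and none are lost in intervention, observed ratio = true ratio / (1 − g). The documents do not give g, so the values below are assumptions. With a true ratio of 1:

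| Assumed g | Null ratio |
|---|---|
| 0 | 1.00 |
| 2.5% | 1/0.975 = 1.03 |
| 5% | 1/0.95 = 1.05 |
| 7.5% | 1/0.925 = 1.08 |

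In patients: the baseline control geometric mean is 14.70 per clinic in 10 months (SAP Table 2). Ten clinics over 18 months give 14.70 × 10 × 18/10 = 264.6 events. This is a low figure, because the geometric mean stands in for the mean. At g = 5% that is 264.6 × 0.05 ≈ 13 patients.

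**4. False-positive rate.** Take SE = SD × √(2/10), noncentrality = ln(ratio)/SE, and a two-sided 5% t test on 17 df (20 clinics less intercept, arm and stratum). At g = 5%, ln(1/0.95) = 0.0513:

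| SD of ln count | SE | Noncentrality | Rejection rate |
|---|---|---|---|
| 0.3 | 0.134 | 0.382 | 6.5% |
| 0.4 | 0.179 | 0.287 | 5.8% |
| 0.5 | 0.224 | 0.229 | 5.5% |

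This is a log-count approximation to the planned Poisson or negative binomial model, without the baseline covariate. The SAP's lower SD of 0.2 is left out. At baseline rates the 18-month counts are 14.70 × 1.8 = 26.5 and 6.49 × 1.8 = 11.7. Poisson variation alone then gives a pooled ln SD of √{(1/26.5 + 1/11.7)/2} ≈ 0.25. Higher enrolment would lower that floor.

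**5. The opposing effect.** If machine grades are read in intervention clinics only, they can also remove cases there: a register positive may prove to be an unrepeated trace in an HIV-negative patient. With a share h removed, the ratio becomes (1 − h)/(1 − g). Section 4.4.3 expects 10–20% trace among Ultra positives. Assume the same share among treated cases, half of them HIV-negative, and half of those unrepeated and ungraded on paper. Then h = 0.10 × 0.5 × 0.5 to 0.20 × 0.5 × 0.5 = 2.5% to 5%.

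- g = 5%: 0.975/0.95 to 0.95/0.95 = 1.03 to 1.00.
- g = 2.5%: 0.975/0.975 to 0.95/0.975 = 1.00 to 0.97.

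Both halves are assumptions. The range includes no effect and effects in either direction.

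**6. Separate, secondary: missing Xpert dates.** For time-to-diagnosis, the definition gives the hub machine date (control) and the treatment start date (any confirmed case lacking a result date). The double-asterisk footnote to the outcome table gives the next transport date (control) and the day after collection (intervention). No order is stated. This does not touch the primary outcome.

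**The case against.** The strongest reply is that the operative text already settles the matter: the numerator is number diagnosed, its list is complete and unrestricted, and the bracket looks like a leftover. Harm needs an analyst to override that list. The route to bias is also narrow. A lost control event must have been treated within 14 days with no positive in any of four paper sources, after the follow-up calls to clinics that the protocol (Data Management) schedules for each two-week extract. Smear-positive control patients need no machine data, and an Xpert result that led to treatment will usually be on paper. All of this stands, and it is why the point is an ambiguity to reconcile and not a demonstrated bias.

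A reader might infer more than the documents support:

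- **That the trial favours the intervention.** An extra source can add events in one arm, but step 5 shows that the net effect could be nil or reversed.
- **That no planned analysis bears on it.** The planned day-14 count of all patients treated for TB needs no test confirmation, so the bracket does not affect it. It is a partial check only, since it can diverge from the confirmed count for other reasons. Neither trace sensitivity analysis varies the data source.
- **That related definitions widen the problem.** Number tested accepts a result "or with a test result recorded in the onsite GeneXpert machine", but it feeds no listed outcome. Date enrolled may use "NTLP Treatment register or machine data", but with no arm limit, so it does not depend on the bracket.

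**Conclusion.** The contradiction is certain on the current text, and it sits in the definition of the primary event. Its effect is not established in size or direction. It is zero if the unrestricted list is used, and possibly near zero even if the bracket is followed. The illustrative figures (null ratio 1.05; false-positive rate 5.5–6.5% at SD 0.5–0.3) rest on an assumed g of 5%, no offset from trace grading, and a log-count approximation. The documents do not show which rule was applied. It should be fixed because the arms could be ascertained differently and the correction is very cheap. The missing-date conflict is real but secondary.

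**What to change.** 1. Delete the bracketed restriction. State one source list for both arms (registers, requisition forms, onsite or hub machine data) and use it in both microbiologically-confirmed TB and number diagnosed.
2. Take Ultra semi-quantitative grades from the same sources in both arms.
3. Report by arm the number of primary events confirmed only in machine data. If that number is zero or trivial, the matter is closed.
4. Hub data are to be sought but are not assured, so deleting the bracket may not fully equalise ascertainment. Run the primary model once more on registers and forms only, in both arms. Treat this as a check and not a replacement: it will miss some true cases, and paper completeness may itself differ by arm.
5. Separately, put the missing-Xpert-date rules for time-to-diagnosis into one stated order.

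The cost is a few words of SAP text, some matching of hub records that the SAP already plans to seek for control dates, and one extra model run.
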